### **5.2.16        Intraocular Pressure (IOP)**

IOP measurements will be performed in both eyes at every study visit except on treatment day (Day 0), where there will be a pre- and post-injection IOP measurement in the study eye only. After the intravitreal injection, the patient will remain in the supine position and IOP will be monitored for at least 30 minutes. In the event that the intraocular pressure is 30 mmHg or above, it will be managed according to Section 5.3.2.

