### **5.3.2 Management of Post Injection Intraocular Pressure**

The investigator shall have the ability to determine the optimum management of a raised intraocular pressure and may use any combination of topical IOP-lowering medications, oral acetazolamide or anterior chamber paracentesis in order to normalize the intraocular pressure.

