11.2 PRIMARY OCULAR SAFETY MEASUREMENTS

The following visual function measures at 6 months are considered primary safety endpoints. They will be listed and summarized by treatment group separately in each phase.

- Change from baseline in visual acuity in the study eye
- Change from baseline in full field sensitivity in the study
- Change from baseline in ambulation
- IOP measurements in the study eye
- Changes from baseline in anatomical parameters as measured in the study eye by:
 - Fundus photography - Qualitative assessment of the retinal appearance
 - Spectral domain-OCT (SD-OCT) - Qualitative assessment of the retinal cross-sectional appearance

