Retina Periphery	Retinal Hemorrhage Retinal Tear Rhegmatogenous retinal detachment, macula center attached Rhegmatogenous retinal detachment, macula center detached Tractional retinal detachment, macula center attached [Tractional retinal detachment, macula center detached Exudative retinal detachment, macula center attached Exudative retinal detachment, macula center detached Other retinal detachment Round (Atrophic) Retinal Hole Lattice Degeneration Other	Not Applicable

^aSeverity for Vitreous flare and Vitreous Haze are included before or after ' ; ' , respectively.

The findings from both ocular biomicroscopic and ophthalmoscopy examinations with prespecified terms will be coded using MedDRA, version 21.0 or newer.

Descriptive statistics for IOP measurements and changes from the baseline values at each visit will be presented by treatment group separately for each phase.

Similarly, descriptive statistics for cup/disc ratio measurements from ophthalmoscopy examination and changes from the baseline values at each visit will be presented by treatment group separately for each phase.

The number and percent of patients with more than one grade increase from baseline for any findings will be summarized by preferred term and by treatment group separately for each phase.

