15.0 DATA HANDLING CONVENTIONS

15.1 SUMMARY STATISTICS

The following statistical summaries will be presented for each type of data. Further details are specified in the tables, figures, and listings shells.

- Continuous variables will be summarized by descriptive statistics (number of patients, mean, standard deviation (SD), median, Q1, Q3, minimum, and maximum values).
- Categorical variables will be summarized by frequency distributions (counts and percentages).
- The results for ocular related assessments in the fellow eye will be summarized across the treatment groups, if applicable.

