15.2 VISIT TIME WINDOWS

[Table 15.2–1](#) presents the visits assigned for efficacy and safety analyses and the corresponding range of treatment days (window) during which an actual visit may occur.

Table 15.2–1. Visit Time Windows

Derived Visit	Scheduled Visit (Target Day^a)	Window
Baseline	Day -45 to 0	Days < 0
Day 0	Treatment Visit (Day 0)	Day 0
Day 1	Post Injection Visit (Day 1)	Day 1
Day 7	Day 7 (7)	Days (2, 12)
Month 1	Month 1 (30)	Days (13, 47)
Month 3	Month 3 (91)	Days (48, 135)
Month 6	Month 6 (183)	Days (136, 230)
Month 9	Month 9 (274)	Days (231, 317)
Month 12	Month 12 (365)	Days (318, 412)
Month 18	Month 18 (548)	Days (413, 682)
Month 24	Month 24 (731)	Days (683, 778)
Month 36	Month 36 (1096)	Days (779, 1413)
Month 48	Month 48 (1461)	Days (1414, 1508)
Month 60	Month 60 (1826)	Days (1509, 2144)

Month 72	Month 72 (2192)	Days (2145, 2238)
Month 84	Month 84 (2557)	Days (2239, 2874)
End of study ^b	Final or Termination Visit	

a Relative to the date of the first dose of study treatment. Day 0 = the date of the first dose of study treatment.

b Presented in summary tables for all visit-based parameters.

If the assessment date (if the assessment date is unavailable, use visit date instead) is on or after the date of the first dose of study treatment, the study day is calculated by assessment date – date of the first dose of study treatment + 1. If the assessment date is before the date of the first dose of study treatment, the study day is calculated by assessment date – date of the first dose of study treatment. Therefore, a negative day indicates a day before the start of the study treatment.

If a patient has 2 or more visits within the same window, the last visit with a non-missing value will be used for analysis.

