15.4 REPEATED OR UNSCHEDULED ASSESSMENTS OF SAFETY PARAMETERS

If a patient has repeated assessments before the start of the first treatment, the results from the final non-missing assessment made prior to the start of the study treatment will be used as baseline. If end-of-study assessments are repeated or if unscheduled visits occur, the last non-missing Post-treatment assessment will be used as the end-of-study assessment for generating summary statistics. However, all Post-treatment assessments will be used for PCS value determinations, and all assessments will be presented in the data listings.

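### The by-visit IOP summary can drop an earlier high study-eye reading, and the SAP has no all-readings count of IOP to recover it

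*SAP*

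**What the plan says.** SAP 11.4 gives the planned analysis of study-eye IOP across visits: "Descriptive statistics for IOP measurements and changes from the baseline values at each visit will be presented by treatment group separately for each phase". SAP 15.1 defines those statistics, which include "median, Q1, Q3, minimum, and maximum values". IOP at 6 months also stands in SAP 11.2, whose list opens "The following visual function measures at 6 months are considered primary safety endpoints".

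SAP 15.2 decides which reading enters a by-visit row: "If a patient has 2 or more visits within the same window, the last visit with a non-missing value will be used for analysis". SAP 15.4 adds that "all Post-treatment assessments will be used for PCS value determinations", and that every assessment is listed. Potentially clinically significant (PCS) criteria are set for laboratory tests (Table 11.6-1) and vital signs (Table 11.7-1). Neither table contains IOP.

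For the injection day, Protocol 5.2.16 says "there will be a pre- and post-injection IOP measurement in the study eye only", followed by at least 30 minutes of monitoring. It then sets an action level: "In the event that the intraocular pressure is 30 mmHg or above, it will be managed according to Section 5.3.2". Under Protocol 5.3.2 the investigator "may use any combination of topical IOP-lowering medications, oral acetazolamide or anterior chamber paracentesis".

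**The concern.** A pressure excursion is an event at a moment, and a by-visit summary shows it only if the reading from that moment is the one kept. The protocol foresees such moments. It monitors pressure after the injection, names a level that calls for management, lets the investigator add visits (6.2), and provides for treatment of intraocular inflammation (6.2.1). A patient seen for raised pressure and seen again once it has settled has two visits in a window, and the summary keeps the second.

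For laboratory values and vital signs the SAP guards against this loss by counting patients over all post-treatment values. In a first-in-human intravitreal study, pressure in the injected eye has no such count. With about three patients per dose group, one lost excursion is a third of the group.

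**Working it through.** The plan gives no figure to reproduce: the sample size is empirical and no IOP rate is assumed.

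**1. Window widths (SAP Table 15.2-1; width = last day − first day + 1)**

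| Row | Days | Width |
|---|---|---|
| Day 0 | 0 | 1 |
| Day 1 | 1 | 1 |
| Day 7 | 2–12 | 11 |
| Month 1 | 13–47 | 35 |
| Month 3 | 48–135 | 88 |
| Month 6 | 136–230 | 95 |
| Month 18 | 413–682 | 270 |
| Month 36 | 779–1413 | 635 |

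The windows leave no gap between them, so an unscheduled visit falls in the window of a scheduled one. If the scheduled visit comes later, the unscheduled reading is not analysed. If unscheduled visits were instead left out of the windows, the reading would still be missing from the by-visit table.

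**2. Study day.** The text of 15.2 computes study day on or after dosing as date difference + 1. The table footnote makes the dosing date Day 0. The two conventions assign early visits differently:

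| Visit | Date difference | Footnote: row | Formula: study day and row |
|---|---|---|---|
| Injection | 0 | Day 0 | 1, Day 1 row |
| Day 1 | 1 | Day 1 | 2, Day 7 row |
| Day 7 (±1) | 6–8 | Day 7 | 7–9, Day 7 row |

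Under the formula the Day 0 row is empty. The true Day 1 and Day 7 visits share the Day 7 row, and the Day 7 value is kept. Under the footnote there is no collision. Under either convention the injection-day readings are alone in a one-day window, so no later scheduled visit replaces them.

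**3. Day 0.** That visit yields a pre-injection reading and one or more post-injection readings. The pre-injection reading can be the baseline (SAP 11.0, last non-missing value before dosing), and its date also places it in the same row as the post-injection readings. No SAP sentence separates them or says which one is analysed.

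**4. Other places where an excursion could appear**
- PCS counts: laboratory tests and vital signs only.
- Count of increases of more than one grade (11.4): covers graded findings; IOP has no grade in Tables 11.4-1 or 11.4-2.
- Ocular TEAE tables (11.1): only if the investigator reports an adverse event; no IOP value makes reporting mandatory.
- Concomitant medication and procedure summaries (8.0): may show the treatment, not the pressure.
- Listings (15.4): all readings.

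**5. Illustration, all pressures assumed.** One patient has a high reading at an unscheduled visit and 16 mmHg at a later visit in the same window; the others have 15 mmHg.
- Group of 3, last visit kept: mean (15 + 15 + 16)/3 = 15.3, maximum 16.
- Same group with the high reading in place: for 30 mmHg, (15 + 15 + 30)/3 = 20.0; for 45 mmHg, (15 + 15 + 45)/3 = 25.0. Maximum 30 to 45; patients at or above 30 mmHg, 1/3 = 33%.
- Group of 12, last visit kept: mean (11 × 15 + 16)/12 = 15.1, maximum 16. The all-readings count would be 1/12 = 8.3%.

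If the high reading is the last or only one in its window, the by-visit maximum does show it.

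**The case against.** The strongest reply is that little is truly lost. Every reading is listed, a spike can be reported as an ocular adverse event and tabulated, drops and paracentesis can appear in the medication and procedure summaries, and in a group of three the minimum, median and maximum are the three retained values. The criterion for calling the therapy safe is the absence of a related adverse event of grade 3 or greater, not mean IOP. Table specifications are in a separate document and might include a threshold table.

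Much of this stands, and it rules out three stronger readings.
- A reader might infer that pressure spikes are counted nowhere. The routes just named show otherwise, though none is a systematic count of pressure.
- A reader might infer that a Day 0 spike is overwritten by the reading taken after treatment. The last-value rule concerns visits, and Day 0 is one visit. The SAP states no choice among readings within it, so that substitution is possible but not planned.
- A reader might infer that the 30 mmHg level and the primary measure concern the same assessment. The primary IOP measure is at Month 6; the level stands in the injection-day text.

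The reply does not reach the stated rule. The maximum in 15.1 is taken over retained values, so it cannot show a reading that 15.2 has removed. The unseen table specifications may add a table, but they do not change the rule in the SAP.

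**Conclusion.** The point holds in a limited form. As written, the SAP can remove an earlier high study-eye reading from the only planned numerical summary of IOP, and it has no worst-value, threshold or all-readings analysis to bring it back. Under the date-difference-plus-one formula this extends to the scheduled Day 1 visit; under the footnote it does not. Day 0 has a separate defect: pre- and post-injection readings are not distinguished.

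The size is one patient in three (33%) of a Phase 1 group, or one in twelve (8.3%) of a full Phase 2a group, for each excursion lost. The means of 15.3 against 20.0 to 25.0 mmHg rest on assumed pressures and on a later visit falling in the same window; the documents give no rate for either. It does not follow that excursions would go unrecorded, that the Month 6 primary measure hides Day 0 spikes, or that the plan's definition of safe is biased. The change should be made, because the SAP already applies the better method to laboratory tests and vital signs.

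**What to change.** In SAP 11.4, add one table by dose group and phase for the study eye:
- each patient's maximum post-injection IOP and maximum change from baseline;
- the number and percent of patients with any recorded post-injection reading of 30 mmHg or above.

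Use all recorded readings, including unscheduled visits, and extend the all-values rule in 15.4 to IOP. The 30 mmHg level serves only as a descriptive cut-off taken from the protocol's Day 0 text; it sets no clinical rule for later visits.

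Show Day 0 as separate pre-injection and post-injection rows. In 15.2, reconcile the study-day formula with the footnote that makes the dosing date Day 0.

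The cost is SAP wording and one table on readings already collected. One limit remains: the protocol does not say that each reading in the 30-minute monitoring is recorded, so a Day 0 maximum can use only what the CRF captures. The SAP is still written to Amendment 2, and Protocol 11.3.6 requires the analysis plan to be final before database lock, so the change can go into the same revision.

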### Grading of Vitreous haze

Consistent with Nussenblatt RB, Palestine AG, Chan CC et al. Standardisation of vitreal inflammatory activity in intermediate and posterior uveitis ([Nussenblatt et al, 1985](#)).

Grade	Vitreous flare	Vitreous Haze	Clinical finding
0	None	No haze	Clear view of optic nerve
1	Minimal	Trace	Slight blurring of optic disc margin
2	Mild	1+	Slightly blurred optic nerve and vessels
3	Moderate	2+	Moderately blurred optic nerve and vessels
4	Marked	3+	Optic nerve head border blurry but visible
5	Severe	4+	Optic nerve head obscured

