11.4 OTHER OCULAR SAFETY MEASUREMENTS

Other ocular safety measurements include the following assessments during the core study visits and clinic visits of the long-term follow-up visits:

- IOP measurements in the study eye (other assessment at month 6 which is the primary endpoint)
- Findings in the study eye from ocular biomicroscopic examination (Table 11.4-1)
- Findings in the study eye from ophthalmoscopy examination (Table 11.4-2)

Table 11.4–1. Findings and Severity from Ocular Biomicroscopic Examination

Biomicroscopic Eye Area	Findings	Severity^a
Eyelids/eyelid margins/lashes	Erythema Edema Crusting Other	+0.5 (Trace) +1 (Mild) +2 (Moderate) +3 (Severe) Not Applicable
Conjunctiva (bulbar or palpebral)	Hyperemia Edema Subconjunctival Hemorrhage Discharge Blanching Follicles Pterygium, encroaching on visual axis Pterygium, not encroaching on visual axis Other	+0.5 (Trace) +1 (Mild) +2 (Moderate) +3 (Severe) Not Applicable
Cornea: • Central Cornea • Peripheral Cornea • Central and Peripheral Cornea	Punctate Epithelial Staining Filaments Infiltrates Edema Corneal Guttata Endothelial Pigment Keratic Precipitates Neovascularization Opacity/Opacities Stromal Haze Other	+0.5 (Trace) +1 (Mild) +2 (Moderate) +3 (Severe) Not Applicable
Anterior chamber	Cells Flare Anterior Synechiae Hypopyon, Details and Levels (mm) Hyphema, Details and Levels (mm) Other	0 (<1 cell, None) +0.5 (1-5) +1 (6-15, Faint) +2 (16-25, Moderate) +3 (26-50, Marked) +4 (>50, Intense (including fibrin)) Not Applicable
Iris/pupil	Rubeosis Iridis, anterior chamber angle involved Rubeosis Iridis, anterior chamber angle not involved Afferent Pupillary Defect (APD) Other	Not Applicable

^aSeverity for Anterior chamber cells and flare are included before or after '/', respectively.

Table 11.4–2. Findings and Severity from Ophthalmoscopy Examination

Ophthalmoscopy Eye Area	Findings	Severity^a
Optic Nerve	Cup/Disc Ratio (Value range 0.0 - 1.0)	Not Applicable
Vitreous	Cells Vitreous Haze Vitreous Hemorrhage Posterior Vitreous Detachment Other	+0.5 (None, No Haze) +1 (Minimal, Trace) +2 (Mild, 1+) +3 (Moderate, 2+) +4 (Marked, 3+) +5 (Severe, 4+) Not Evaluable Not Applicable
Optic Nerve	Disc Hemorrhage Other	Not Applicable
Macula	Intraretinal Fluid Subretinal Fluid Intraretinal Hemorrhage Subretinal Hemorrhage Rhegmatogenous Detachment Tractional Detachment Pigment Epithelial Detachment Other	Not Applicable
Fundus	Other	Not Applicable

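### SAP 11.4 counts eye-examination findings only by a rise of more than one grade, which 22 named ungraded findings, including retinal tear and detachment, can never meet

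*SAP*

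**What the plan says.** SAP 11.4 sets out its scope as follows: "Other ocular safety measurements include the following assessments during the core study visits and clinic visits of the long-term follow-up visits". Tables 11.4-1 (biomicroscopy) and 11.4-2 (ophthalmoscopy) list the findings by eye area with a severity column. Findings from both examinations "with prespecified terms will be coded using MedDRA, version 21.0 or newer". The section then gives its only count: "The number and percent of patients with more than one grade increase from baseline for any findings will be summarized by preferred term". The other summaries in 11.4 are descriptive statistics for IOP and for cup/disc ratio.

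The severity columns differ by eye area:

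- **Iris/pupil, optic nerve, macula, fundus and retina periphery:** Not Applicable is the only entry. This covers lines such as "Rhegmatogenous retinal detachment, macula center detached".
- **Lids, conjunctiva and cornea:** the levels are "0.5 (Trace) +1 (Mild) +2 (Moderate) +3 (Severe) Not Applicable", with nothing below Trace.
- **Anterior chamber:** the scale opens with "0 (<1 cell, None) +0.5 (1-5) +1 (6-15, Faint", so it does have a level for none.
- **Vitreous:** the scale also has a level for none.

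Baseline is the last non-missing assessment before dosing (SAP 11.0). The SAP does not say what grade an absent finding takes, or whether one grade means one numeric unit or one step on the scale.

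**The concern.** The rule is written for any findings, yet it needs a grade at both time points. An ungraded retinal detachment that appears after injection cannot show a grade increase, so the count for that term is zero whatever the examiner saw. Tears, detachment and hemorrhage are complications of the injection that the protocol itself names (3.11.1.1 and 6.2.2), and detachment is its example of significant ocular toxicity (7.4).

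For graded findings the problem is reproducibility. Two programmers following the same sentence could count new corneal or anterior chamber findings differently. Keratic precipitates and anterior chamber cells, both affected, were among the findings in the dog study (Protocol 3.6.2.1).

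The table matters most in long-term follow-up. Protocol Table 3 schedules visual acuity and the complete ophthalmic examination there, and no fundus photography or SD-OCT.

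**Working it through.** The plan gives no figure to reproduce. The check is a count from Tables 11.4-1 and 11.4-2, followed by applying the rule to a new finding.

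**1. Entries whose only severity is Not Applicable**

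| Eye area | Named | Other | Total |
|---|---|---|---|
| Iris/pupil | 3 | 1 | 4 |
| Optic nerve | 1 | 1 | 2 |
| Macula | 7 | 1 | 8 |
| Fundus | 0 | 1 | 1 |
| Retina periphery | 11 | 1 | 12 |
| Sum | 22 | 5 | 27 |

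Cup/disc ratio is left out because it has its own summary.

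**2. What the 22 named findings are**

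- Detachment: 3 macular (including pigment epithelial) + 7 peripheral = 10.
- Tear: 1.
- Hemorrhage: 1 disc + 2 macular + 1 peripheral retinal = 4.
- Subtotal: 10 + 1 + 4 = 15.
- The remaining 7: rubeosis 2, afferent pupillary defect 1, macular fluid 2, round hole 1, lattice degeneration 1.

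The 27 is a minimum. The anterior chamber and vitreous rows carry both a scale and Not Applicable. Suppose, as an assumption, that seven of their entries are recorded as Not Applicable: synechiae, hypopyon, hyphema and Other; vitreous hemorrhage, posterior vitreous detachment and Other. The total would then be 27 + 7 = 34.

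**3. A new lid, conjunctival or corneal finding, under three readings of the rule**

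| New finding at | Absent has no value | Absent = 0, numeric rise | Absent = 0, scale steps |
|---|---|---|---|
| +0.5 Trace | undefined | 0.5, not counted | 1, not counted |
| +1 Mild | undefined | 1, not counted | 2, counted |
| +2 Moderate | undefined | 2, counted | 3, counted |
| +3 Severe | undefined | 3, counted | 4, counted |
| Levels counted | 0 of 4 | 2 of 4 | 3 of 4 |

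These rows hold 4 + 9 + 11 = 24 entries (21 named, 3 Other). That is an upper bound on the graded entries affected, because these columns also allow Not Applicable and the tables do not tie severities to individual findings.

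**4. Anterior chamber cells**

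A rise from 0 to +1 is 1 numeric unit (not counted) but 2 steps (counted). From a baseline of 0, the rule counts 3 of the 5 higher levels by numeric difference (+2, +3, +4) and 4 of 5 by steps. Flare has no half-grade in Protocol Table 4, so the two readings agree.

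**5. Vitreous**

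The SAP codes the clear state as "0.5 (None, No Haze", while the protocol's vitreous scale gives grade 0 to "Clear view of optic nerve". None to Trace is 1 − 0.5 = 0.5 (SAP) or 1 − 0 = 1 (protocol), counted under neither. None to Mild is 2 − 0.5 = 1.5 or 2 − 0 = 2, counted under both. The mismatch changes no count under this rule.

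**The case against.** **A grade rule naturally covers only graded findings.** SAP 15.1 has categorical variables summarized by counts and percentages and refers to the shells for detail, so the ungraded findings may already have a table. This stands in part: the shells could settle the matter and were not available. But 15.1 states no count of newly present findings. If any findings is read as graded findings, SAP 11.4 states no count at all for the other 22.

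**The events are displayed elsewhere.** Ocular adverse events in the study eye are tabulated by preferred term and by severity (SAP 11.1). Fundus photography and SD-OCT are listed and summarized at Month 6 and by visit (SAP 11.2 and 11.3). All assessments are listed (SAP 15.4), and ocular inflammation is reported to the DSMC (Protocol 6.1.1.2). With up to approximately 21 patients, a listing shows every event. This stands and is why the point is minor. It does not repair the table. Imaging is not scheduled in long-term follow-up, and the adverse-event route depends on reporting. SAP 11.9.1 sends new or worsened physical examination findings to the adverse event form, but the SAP states no such rule for eye-examination findings.

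**The Other lines are not prespecified terms.** This stands. The figure to rely on is 22, with 27 as the count of form entries.

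**Conclusion.** The point holds and is minor. The one stated count in SAP 11.4 cannot register 22 named findings (27 entries with Other), 15 of which are tear, detachment, or disc, macular or retinal hemorrhage. For lids, conjunctiva and cornea, a new finding has no defined grade increase. This rests on reading the severity columns as printed and on the shells not overriding the text.

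A reader might infer more than the documents support:

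- **That new detachments would go unseen, or that a safety decision would be affected.** They would not be lost. Such signs meet the adverse event definition in Protocol 8.1.1. The safety criterion (SAP 5.0) is defined by adverse events, and none of the stopping and escalation rules (Protocol 7.4) uses this table.
- **That every hemorrhage is excluded.** Vitreous and subconjunctival hemorrhage sit in rows that have a severity scale.
- **That all 24 lid, conjunctival and corneal entries are graded.** Their columns also allow Not Applicable.
- **That scale steps are the correct reading.** Nothing in the documents favors steps over numeric units.

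**What to change.** In SAP 11.4:

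1. For findings recorded without a severity grade, report by treatment group and phase the number and percent of patients with the finding absent at baseline and present at any post-treatment visit, including the long-term follow-up clinic visits.
2. For graded findings, treat absent as 0 where the scale has no absent level, and state one reading of grade increase, numeric unit or scale step. The choice is the sponsor's and should be fixed before database lock. The threshold of more than one can stay. No recoding of the vitreous scale is needed for this purpose.
3. Check that the table shells match.

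The cost is one SAP paragraph and one more descriptive table from data already collected. The table will also show incidental findings such as lattice degeneration. If the sponsor chooses scale steps, new mild findings such as conjunctival hyperemia, a common injection effect (Protocol 6.2.2), will be counted; under numeric units they will not. Protocol 11.3.6 has the analysis plan finalized before the single lock. The SAP is still written to Amendment 2, so this can go into an update that is needed anyway.
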